The study design is an open-label, randomized controlled trial. The study will be conducted at study sites in Uganda and South Africa. The study population will include HIV-infected patients on first-line antiretroviral therapy with a recent viral load >1,000 copies/milliliter (mL). Eligible participants will be randomized to the WHO-based standard of care for management of virologic failure or immediate resistance testing with use of results to guide ART regimen decisions. The study will add the use of a diagnostic test, HIV-1 RNA resistance testing to clinical management of participants in the resistance testing arm, but all other clinical care including provision of ART therapy will be done by clinic sites in keeping with local HIV guidelines. The primary outcome of interest will be viral suppression (<200 copies/mL) at 9 months after study enrollment, and will be assessed using an intention to treat analysis, where missing or absent results will be considered failures. Secondary outcomes of interest will be viral suppression below the limit of assay detection, viral suppression on continuation of first-line (non-nucleoside reverse transcriptase inhibitor [NNRTI]-based) therapy, drug resistance at study conclusion, and mortality, among others. We will analyze primary data collected during the trial to conduct an economic analysis with the goal of estimating the cost-effectiveness of resistance testing versus standard of care.

B. Study Sites

1. Uganda

The Immune Suppression Syndrome (ISS) clinic at the Mbarara Regional Referral Hospital (MRRH) and its partner clinic across the street, the **Mbarara Municipal Clinic**, are PEPFAR-supported clinics, which, in combination, follow more than 20,000 patients with HIV/AIDS and have an established clinical research infrastructure. The clinics employ over 50 clinical care staff including nurses, clinicians, pharmacists, counselors, phlebotomists, patient trackers, and administrative staff. The clinics serve as the primary research sites for the MGH-MUST Global Health Collaborative, which employs an additional 60 research staff with expertise in recruitment, enrollment, participant monitoring, informed consent, data collection, phlebotomy, and laboratory storage and testing.

2. South Africa

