In Durban, participants will be recruited from the **Addington Hospital Sinathando HIV Clinic, Clairwood Hospital HIV Clinic, Wentworth Clinic, and King Dinizulu Hospital**. The four clinics together manage an active caseload of over 10,000 HIV patients. The study will be managed centrally from the University of KwaZulu-Natal (UKZN), which operates numerous HIV clinical research projects and employs research staff with experience in recruitment, enrollment, participant monitoring, informed consent, data collection, phlebotomy, and laboratory processing, storage, and testing.

C. Eligibility Criteria

We will recruit persons with HIV-infection who are in care at any of the five above clinics who meet the following inclusion criteria:

1. Inclusion criteria:

- a. In care at a public HIV clinic within a PEPFAR-focus sub-Saharan African country (South Africa or Uganda) and living within 100 kilometers of the clinic
- b. Age \geq 18 years at the time of enrollment
- c. Currently prescribed first-line (non-nucleoside reverse transcriptase inhibitor [NNRTI]-based) ART for at least 5 months. Switches within first line regimens, including NNRTI and nucleos(t)ide backbone changes are allowed.
- d. Detectable plasma viral load $>$ 1,000 copies/mL and/or dried blood spot viral load $>$ 1,000 copies/mL within 90 days of enrollment

2. Exclusion criteria:

- a. Known prior drug resistance
- b. Prior exposure to PI-based ART
- c. Current clinical indication to start PI-based ART
- d. Not planning to remain in the clinic catchment area for the next nine months

3. Eligibility criteria rationale

The study aims to enroll HIV-infected adults on first-line ART with a newly identified instance of a viral load $>$ 1,000 copies/mL. Patients attending study clinics implementing dried blood spots (DBS) for

virologic testing will be eligible, provided they have a DBS viral load >1,000 copies/mL [25, 26], or if they undergo repeat plasma viral load testing to confirm a viral load >1,000 copies/mL. We aim to exclude those with known prior resistance, those on second line therapy, and those at high risk for default from study because of immigration out of the clinic catchment area.

D. Recruitment and Enrollment

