management issues, the site principal investigators ([name] in Mbarara and [name] in Durban) will be contacted to offer input. At the conclusion of Visit 2B-SOC, participants in the SOC arm will be scheduled for a final study visit approximately 9 months after enrollment. A final visit at this time is chosen to allow ample time for drug suppression for participants with detectable viral load, and to ensure balance in observation time between study arms. Non-study clinical visits for routine clinical care and adherence counseling recommendations will continue in the interim as determined and scheduled by clinic staff.

D. Visit 3: Outcome Assessment

At Study Visit 3, participants will undergo repeat blood testing for plasma viral load and, if the viral load is detectable, reflex resistance testing will be performed. An additional 10cc tube will be drawn for storage for future testing for viral load, resistance testing, and drug therapeutic monitoring. A voided urine specimen will also be collected for future testing for therapeutic drug monitoring. A study questionnaire will be administered to assess resource allocation, ART medication adherence, and quality of life. Study staff will review participant records to update interim CD4 count, viral load, and ART regimen data. Results of viral load and resistance testing from this visit will be immediately made available to clinic staff for further patient management. At the conclusion of Visit 3, study procedures will be complete.

E. Missing and Late Appointments

If study participants do not present for study visits, study staff will call them to encourage return to clinic for continuation or completion of procedures. For participants who do not return within 7 days of a scheduled visit and unreachable by phone, a study staff member will attempt to track them at home using a standardized lost-to-follow-up form and procedures developed and used successfully both for program and clinical care in Mbarara for over 10 years [32, 33]. If participants are located, study staff will encourage them to return to clinic to complete procedures and/or conduct the blood draw and questionnaire in the field if the participant agrees.

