During the COVID-19 pandemic, participants who do not present for regularly-scheduled HIV clinic appointments will be phoned when contact information is available. Rather than tracking at home for participants that cannot be reached, tracking will be delayed until the COVID-19 pandemic subsides and regularly scheduled study procedures can resume.

VI. STUDY PROCEDURES FOR PARTICIPANTS RANDOMIZED TO RESISTANCE TESTING ARM

A. Visit 1-RT: Baseline Visit for Resistance Testing Participants

At Study Visit 1, participants randomized to the RT will complete the baseline questionnaire to collect sociodemographic, HIV clinical and treatment history, self-reported ART medication adherence, quality of life, and resource allocation data. Study staff will review participant records to collect data on clinic initiation start date, opportunistic infection history, ART initiation date, ART regimen history, CD4 count and viral load result histories. Upon completion of the baseline questionnaire, participants will undergo phlebotomy for resistance testing. Participants will be notified that study staff will contact them as soon as their results are available, to request return to clinic for further management. A voided urine specimen will also be collected for future testing for therapeutic drug monitoring. Upon completion of the study procedures, participants will be referred to clinic counselors who will conduct adherence support

counseling as per standard clinical procedures. The participant will be instructed to continue their current ART regimen until at least the next clinical visit. When the resistance test result is available, study participants will be contacted by phone and requested to return to clinic for review.

B. Visit 2-RT: Resistance Testing Results and Therapeutic Management

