At Study Visit 2-RT, study clinicians will review the resistance testing result. A study HIV-1 RNA drug resistance interpretation guide will be used to help guide decision-making. Participants without significant drug resistance, as determined by the study clinician in consultation with the resistance interpretation guide and, if needed, study investigators will continue their first-line (NNRTI-based) ART regimen without change. Participants will be referred to clinic counselors for adherence support. Participants with meaningful therapeutic drug resistance will change ART regimen to a second-line, protease inhibitor (PI)-based or, if available, integrase inhibitor (II)-based therapy. Clinicians will also be encouraged to change the nucleos(t)ide reverse transcriptase component of the regimen (for example, changing from zidovudine to tenofovir). All regimen decisions will be made by the study clinician, in cooperation with clinic staff at the study sites. In the case of complex management issues, the site principal investigators ([name] in Mbarara and [name] in Durban) will be contacted to offer input. At the conclusion of Visit 2-RT, participants will be scheduled for a final study visit approximately 9 months later. A final visit 9 months later is chosen to match the approximate 9-month study duration for participants in the SOC arm. Non-study clinical visits for routine clinical care will continue in the interim as determined and scheduled by clinic staff.

C. Visit 3: Outcome Assessment

At Study Visit 3, participants will undergo repeat blood testing for plasma viral load and, if the viral load is detectable, reflex resistance testing will be performed. An additional 10cc tube will be drawn for storage for future testing for viral load, resistance testing, and drug therapeutic monitoring. A voided urine specimen will also be collected for future testing for therapeutic drug monitoring. A study questionnaire will be administered to assess resource allocation and quality of life. Study staff will review participant records to update interim CD4 count, viral load, and ART regimen data. Results of viral load and resistance testing from this visit will be immediately made available to clinic staff for further patient management. At the conclusion of Visit 3, study procedures will be complete.

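### Read literally, Visit 3 is timed from enrollment in the standard-of-care arm but from the results visit in the resistance-testing arm, contrary to the 9-month endpoint

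*Combined protocol and SAP*

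**What the plan says.** Section IV.A sets the endpoint: "The primary outcome of interest will be viral suppression (<200 copies/mL) at 9 months after study enrollment". Section V.C follows it for the SOC arm: "participants in the SOC arm will be scheduled for a final study visit approximately 9 months after enrollment". It gives two reasons for that time: "to allow ample time for drug suppression for participants with detectable viral load", and "to ensure balance in observation time between study arms". Section X.B.2 also justifies the outcome by a balanced assessment at 9 months from the start of study.

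For the RT arm, section VI.B reads: "At the conclusion of Visit 2-RT, participants will be scheduled for a final study visit approximately 9 months later". The next sentence gives the reason: "A final visit 9 months later is chosen to match the approximate 9-month study duration for participants in the SOC arm". Visit 2-RT is not the enrollment visit. Under section VI.A it comes after the laboratory result: "When the resistance test result is available, study participants will be contacted by phone and requested to return to clinic for review". No turnaround time is given.

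Section X.B.4 counts a participant without a confirmed result at the 9-month endpoint as a failure. Sections VI.C and VII refer to a follow-up window or timeline for Visit 3, and foresee late closure visits because of COVID-19. The text supplied gives that window neither an origin nor a width.

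**The concern.** The two scheduling instructions count 9 months from different starting points. A site that follows each as written reads the primary outcome later in RT than in SOC. That difference comes from the visit calendar, not from the strategy under test. Participants who change regimen in RT would also have more time to suppress before the outcome sample than timing from enrollment would give them, and section V.C treats that time as relevant to the outcome.

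The undefined window adds a second problem. If the analysis used a narrow window around month 9, RT samples drawn on the literal schedule could fall outside it and be counted as failures under section X.B.4. If it used none, late samples would count without any stated limit. In an open-label trial that choice should not be left until viral loads can be compared by arm.

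Two secondary outcomes are exposed as well. Section X.B.3 defines total costs over the duration of the study and retention at study completion, and both would run L months longer in RT.

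**Working it through.** **Inputs**
- Endpoint: 9 months from enrollment (IV.A).
- SOC Visit 3: 9 months from enrollment (V.C).
- RT Visit 3, literal: 9 months from the end of Visit 2-RT (VI.B).
- L = months from enrollment to Visit 2-RT. Not stated; VI.A gives only the order of events.
- SOC repeat viral load: 2 to 3 months after baseline (V.A). Pregnant SOC participants return at about 1 month and are left out of step 2.
- L′ = months from the SOC repeat viral load to the SOC decision at Visit 2B. Not stated.

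**Step 1: Visit 3 measured from enrollment**
- SOC: 9.
- RT, literal: 9 + L.
- RT minus SOC: L. As a share of 9 months, L/9, so 1/9 = 11.1% per month of L.
- For scale only, with L assumed because the document gives no value: L = 0.5, 1 and 2 put RT Visit 3 at 9.5, 10 and 11 months, that is 5.6%, 11.1% and 22.2% later.
- With enrollment as the origin in both arms, the scheduled difference is 0 for any L.

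**Step 2: time between regimen decision and Visit 3**
- SOC: 9 − (2 to 3) − L′, so at most 6 to 7 months.
- RT, literal: 9.
- RT, timed from enrollment: 9 − L.
- RT minus SOC, literal: (2 to 3) + L′.
- RT minus SOC, timed from enrollment: (2 to 3) + L′ − L.
- The two differ by exactly L, whatever L′ is.

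The enrollment-based difference belongs to the strategy: RT reaches its decision without waiting for a repeat viral load. Only the additional L comes from the scheduling sentence.

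**Step 3: which statements the literal schedule contradicts**
- The endpoint time in IV.A: 9 + L is not 9.
- The balance rationale in V.C and X.B.2: the arms differ by L.
- The reason given in VI.B itself: a visit at 9 + L does not match a 9-month SOC duration.

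**Step 4: power**
The stated power does not depend on follow-up time. With 420 × 0.95 = 399 per arm, 68% in SOC and two-sided α = 0.05, a continuity-corrected normal approximation gives 0.684, 0.875 and 0.967 for differences of 8, 10 and 12 points. The plan states 0.69, 0.88 and 0.97. These figures reproduce and are not affected.

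**What cannot be computed**
The document gives no value for L and no rate at which suppression changes around month 9. The size and direction of any bias in the primary comparison therefore cannot be derived.

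**The case against.** The strongest reply is that this is one loose sentence in an otherwise consistent plan. Sections IV.A and V.C count from enrollment, X.B.2 counts from the start of study, and VI.B states its aim of matching SOC in the next sentence. Testing in RT is meant to be immediate, so L may be short enough for the approximate wording to absorb it. The study schema (Figure 2) is not shown and may carry visit times, and section VIII.C says that the database handles scheduling. The window may therefore be defined somewhere the text does not show.

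Most of this stands. It establishes intent, and it means that the absence of a window in the text cannot carry the point alone. It does not remove the conflict: VI.B is the instruction RT staff would work from, and nothing in the text shows which origin they used.

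A reader might infer more than the document supports:
- **That RT outcomes were in fact read later.** No visit dates are given.
- **That the comparison favors RT.** More time after a regimen change could raise suppression, but later visits could also lose more results.
- **That late departures count against RT only.** The exclusion "Not planning to remain in the clinic catchment area for the next nine months" covers nine months, and the literal RT schedule runs past it. But SOC Visit 3 is also only approximately at 9 months, COVID-19 closure visits may be late in both arms, and absent participants are traced, with blood drawn in the field if they agree (V.E, VI.D).
- **That mortality and quality of life share the problem.** Section X.B.3 already fixes both at 9 months.

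**Conclusion.** The point holds as a conflict between operative scheduling instructions, and it should be resolved before the arms are compared. As written, RT Visit 3 falls L months after SOC Visit 3, and RT has L more months after the regimen decision than timing from enrollment would give. Confidence is high for the textual conflict. Whether any real timing difference arose depends on site practice, which the document does not show. The consequence for the primary result is undetermined in both size and direction, and could be negligible if L is short.

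The cost issue is confined to the secondary outcome in X.B.3, because the cost-effectiveness model in X.C.2 already takes trial data for the first 9 months only.

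**What to change.** 1. **Check, then reconcile.** Establish from recorded visit dates which origin the sites used. Then align V.C and VI.B so that Visit 3 is timed from enrollment/randomization in both arms, as IV.A states. Apply this to any Visit 3 still to be scheduled, and document how earlier RT visits were scheduled. The dates come first because enrollment is complete (section VII), and a corrected sentence alone could misdescribe what was done.
2. **One rule for which samples count.** Before viral loads are compared by arm, state which Visit 3 samples are the 9-month result for X.B.4. The rule should be measured from randomization and identical in both arms. It should be wide enough that samples drawn on the literal VI.B schedule, or at COVID-19 closure visits, do not become failures merely for being late.
3. **Report timing.** Give time from randomization to the Visit 3 sample by arm. If it differs, add a supportive sensitivity analysis restricted to sample times that both arms share.
4. **Common cut-off.** Count record-based costs and retention to the same 9 months from randomization in both arms. Mortality needs no change.

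The cost is a corrected sentence, some analysis-plan text and a little more analysis work, with no extra patients, visits or tests. The limits should be stated: items 2 and 3 can describe a timing difference that has already occurred but cannot remove it, and the sensitivity analysis selects on a time determined after randomization.

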Please see the phlebotomy and specimen collection standard operating procedures for full details of specimen collection and processing procedures. In brief, a single blood draw will be performed at relevant study visit to collect whole blood into EDTA tubes (depending on the visit, with a maximum of 15 cc per visit). Tubes will be labeled with pertinent study identifiers, refrigerated until transfer, and/or immediately transferred to the relevant laboratory (based on country) on the day of collection. Approximately 300uL of whole blood will first be removed from EDTA tubes to prepare 5 dried blood spots (~50uL/each) for future drug level testing. Dry blood spot cards will remain at room temperature overnight (minimum 4 hours) to allow drying, and then frozen for future testing. The remainder of the blood will be centrifuged to allow separation of plasma, which will be aliquoted into 1cc aliquots. Specimens will be divided for immediate testing or storage at -80°C.

In addition, voided urine specimens will be collected at the enrollment visit, visit 2A-SOC, and visit 3. For women of under age 50, the urine specimen at the enrollment visit will be used for the urine β -HCG test. Otherwise, and for all other participants, specimen containers will be labeled with pertinent study identifiers, refrigerated until transfer, and/or immediately transferred to the relevant laboratory (based on country) on the day of collection. 1cc of the urine specimen will be aliquoted and stored at -80°C for future testing. Therapeutic drug monitoring will be done in South Africa by Africa Health Research Institute and in the United States by University of California San Francisco and UrSure, Inc.

4. Phlebotomy Schedule

Table 3. Phlebotomy and Urine Collection Schedule

Study Arm	Visit	Tube and Whole Blood Volume	Specimens	Purpose
Standard of Care Arm	Visit 1-SOC	10 cc EDTA	5 X 1cc plasma*	Storage for future single copy viral load and minority resistance testing, and bulk (Sanger) resistance testing
			Dried Blood Spots^	Storage for future therapeutic drug monitoring
		Urine collection	1cc voided urine	Storage for future drug monitoring
	Visit 2A-SOC	4 cc EDTA[#]	2 X 1cc plasma	Viral load testing for ART treatment allocation
		10 cc EDTA	5 X 1cc plasma*	Storage for future single copy viral load and minority resistance testing, and bulk (Sanger) resistance testing
			Dried Blood Spots^	Storage for future therapeutic drug monitoring
		Urine collection	1cc voided urine	Storage for future drug monitoring
	Visit 2B-SOC	None	No blood draw	
	Visit 3	4cc EDTA[#]	2 X 1cc plasma	Viral load and resistance testing for outcome assessment
10cc EDTA		5 X 1cc plasma*	Storage for future single copy viral load and minority resistance testing, and bulk (Sanger) resistance testing	
		Dried Blood Spots^	Storage for future therapeutic drug monitoring	
Urine collection		1cc voided urine	Storage for future drug monitoring	
Resistance Testing Arm	Visit 1-RT	4cc EDTA[#]	2 X 1cc plasma	Resistance testing for ART treatment allocation
		10cc EDTA	5 X 1cc plasma*	Storage for future single copy viral load and minority resistance testing, and bulk (Sanger) resistance testing
			Dried Blood Spots^	Storage for future therapeutic drug monitoring
		Urine collection	1cc voided urine	Storage for future drug monitoring

Visti 2-RT	None	No blood draw	
Visit 3	4cc EDTA[#]	2 X 1cc plasma	Viral load and resistance testing for outcome assessment
	10cc EDTA	5 X 1cc plasma*	Storage for future single copy viral load and minority resistance testing, and bulk (Sanger) resistance testing
		Dried Blood Spots [^]	Storage for future therapeutic drug monitoring
	Urine collection	1cc voided urine	Storage for future drug monitoring

[#]Specimens in bold-faced font will be processed and tested immediately for study purposes. Other specimens will be stored for future testing.

*10cc of whole blood will be centrifuged to prepare approximately 5cc plasma that will be stored as 5 X 1cc aliquots. 3cc of stored plasma will be tested for low copy viral load assay and the remaining 2cc will be used for low copy resistance testing assays. These tests will be done at Harvard Medical School

[^]Dried blood spots will be tested for antiretroviral therapy drug levels to assay for treatment adherence

C. Data Management and Storage

1. Paper Forms. There will be two paper forms used in the study: the Informed Consent Forms and the Tracking Form. Both of these two forms will be stored in locked file cabinets, in locked research offices.
2. Electronic Database. The remainder of study data will be collected and uploaded into the study [REDCap Database](#). REDCap is a password protected, online database application that allows for storage of study data on encrypted servers in the United States. The application includes features for field limits, data quality control, study scheduling, randomization, and real-time study monitoring. Questionnaires and clinical records will be completed in real-time and entered by study staff using encrypted study mobile tablets. The REDCap application allows for both online (real-time) data entry or, when internet service is not available, offline entry with syncing to the server when internet becomes available again.
3. Clinical Records. Records from clinic databases may be entered directly into the database form participant charts or transferred electronically to the study project coordinator for upload into the study database. All data transfers will be done using password-protected, encrypted files, transferred using secure email or encrypted hard drives, and be free of specific patient identifiers including name, dates of birth, or address.

D. Data Protection and Confidentiality

Paper forms that include participant protected health information will be stored on the day of enrollment in participant specific folders within locked file cabinets in locked research offices. Only study staff will have access to the file cabinets. All other study data will be free of identifying information. Data will be stored on an encrypted REDCap Server hosted by Massachusetts General Hospital Research Management in Boston, Massachusetts. Access to the study database both on site and remotely is restricted to study staff and password protected. All study mobile tablets will be password protected and encrypted prior to

study initiation. Data collected on mobile tablets will be uploaded to the server in real-time during data entry, or synced to the server as soon as data/Internet access becomes available if it is not during data entry, using the REDCap Offline Application.

IX. STUDY MONITORING AND QUALITY ASSURANCE

A. Staff Trainings

1. Research Staff

All research assistants will complete training through the CITI biomedical human subjects research course or a refresher course, as indicated. Only research staff fluent in the local languages (Runyankole or IsiZulu) will conduct informed consent and survey procedures. Study staff certified in phlebotomy will complete any blood collection procedures. Study staff will maintain active research ethics certification and attend any annual research ethics conferences as mandated by local policy at their institutions.

2. Clinical Study Staff

Prior to study initiation, clinical study staff will complete a training in the interpretation of HIV-1 resistance testing results and management of virologic failure. The course will be designed and directed by study Co-Investigators Drs. [name], [name], and/or [name] and conducted at the study sites. The course will include a review of major non-nucleoside and nucleos(t)ide reverse transcriptase inhibitor mutations, second-line regimen options, drug-drug interactions, common drug toxicities, and a case-based learning session.

B. Data Monitoring

After review of the study protocol with National Institutes of Health officials, the proposed study is considered to present minimal risk to participants given that subjects will complete questionnaires and undergo routine HIV monitoring with viral load and resistance testing per standard guidelines, and no investigational agents or tests will be used. Therefore, we will not establish a formal Data and Safety Monitoring Board. The study statistician and co-investigators will meet annually to perform the following activities: a) review the research protocol and plans for data and safety monitoring; b) review progress of the trial, including analysis of data quality and timeliness; subject recruitment, randomization and retention; subject risk versus benefit; and other factors that may affect outcome. c) review serious and unexpected adverse event reports, provide commentary, and provide oversight to ensure that reports are relayed to individual IRBs; d) review proposed modifications to the study prior to their implementation. Meetings will be held every twelve months beginning in Year 2 of the study. We will also have an independent data monitor who will annually review blinded summaries of outcome and adverse event data and provide a report to study investigators on recommendations amending the study.

C. Adverse and Unexpected Event Reporting

To identify adverse events: (1) study clinicians will perform a clinical review at each study visit and (2) study staff will instruct participants to report any unexpected or severe adverse events to their assigned research assistant. Such a report will immediately be brought to the attention of study principal investigators. Any adverse events that are unanticipated (i.e. not related to standard HIV clinical care or thought to be directly related to study procedures) or severe (e.g. death) will be brought to the attention

[figure not shown]
of the principal Investigator and reported to participating ethical review committees within 7 days. The relevant committee will determine whether it is appropriate to pause the study or alter the study protocol, and will provide suggestions/modifications to the study procedures as necessary. Possible modifications include adding adverse events to the consent form and re-consenting all study participants. The site principal investigator will be responsible for monitoring participant safety at each site on a monthly basis at regularly scheduled research meetings. They will keep a written log of all events and ensure that the ethical review committee is contacted when necessary. They will also keep a log of the outcome of committee decisions regarding adverse events and apprise the research team of any changes that need to occur as a result of such decisions.

X. STATISTICAL CONSIDERATIONS AND ANALYSES

A. Sample Size

We propose to enroll and maintain a sample size of 840 patients, with approximately 420 randomized to each arm. This sample will enable adequate power to detect a clinically significant, 10% or greater rate of our primary outcome (viral load <200 copies/mL) at study conclusion in the RT arm (see below for power calculation). We have selected this threshold because we predict that a finding of this magnitude would be necessary to advocate for a change in current practice of virologic failure management.

To assess our sample size calculation, we first estimated predicted rates of viral suppression in the SOC arm (Figure 3). To do so, we combined estimated suppression rates for those who remain on first line therapy and those who are switched to second line therapy, due to a persistent elevation in viral load >1,000 copies/mL. Multiple studies have reported that approximately 40% of people (range 27% - 59%) with an initial detectable viral load on first-line therapy load will re-suppress while remaining on first line therapy in the interim [2, 8-10]. Among those who do remain on first-line therapy, we estimate that only approximately 50% will remain suppressed on first-line therapy, owing to both high rates of underlying resistance [8], and sub-optimal adherence. Among patients in the SOC arm with persistent virologic failure on repeat testing who are switched to second line therapy, we expect approximately 80% will re-suppress [35]. In summary, we predict that net re-suppression rates in the standard of care arm compiling those who remain on first-line therapy (20%) and those who switch to second line therapy (48%), will be approximately 68%. While comparative rates of re-suppression with resistance testing are unknown, we hypothesize that resistance testing has the potential to significantly improve viral suppression rates, particularly because rates of resistance at first-line failure are common in the region (65-90%) [7, 8, 36], and because those who are switched to a protease inhibitor-based combination regimen are highly likely to re-suppress [37-39].

Figure 3. Schema of estimated outcomes for participants in the standard of care arm.

Assuming a 68% viral suppression rate in the SOC arm, using a two-sample test of binomial proportions with a Type I error rate of 5%, and allowing for a 5% rate of invalid tests, we compute a 69%, 88%, and 97% power to detect a difference in suppression rates of 8, 10, and 12%, respectively (Table 3). Based on these estimates, we plan to enroll approximately 840 total participants into the study to allow sufficient power to detect a programmatically meaningful 10% superiority rate of viral suppression in the RT arm.

Table 3. Sample Size Estimates

Viral Suppression Rate in SOC Arm	Viral Suppression Rate in RT Arm	Difference in Outcome Rate	α	Sample Size (per group)	Invalid Test Rate	Power
68%	76%	8%	0.05	420	5%	0.69
68%	78%	10%	0.05	420	5%	0.88
68%	80%	12%	0.05	420	5%	0.97

B. Efficacy Analyses

1. Primary Outcome of Interest

Proportion of patients with a laboratory confirmed suppressed viral load, as defined by <200 copies/mL, at study conclusion (Visit 3).

2. Rationale for Primary Outcome of Interest

We have chosen this as our primary outcome to ensure a balanced outcome assessment 9 months after study initiation, standardization of viral load results across sites with different viral load testing platforms, and because it is an accepted international standard for other international studies of virologic suppression [39, 40].

3. Secondary Outcomes of Interest

- a. Proportion of patients with an undetectable viral load (below limit of detection) at study conclusion
- b. Proportion of patients with an undetectable viral load on first-line (NNRTI-based) therapy at study conclusion
- c. Proportion of patients with International AIDS Society-defined drug resistance mutations to their current regimen ^[41]. As part of this analysis, we will also evaluate for minority drug resistance.
- d. Total patient care costs, including diagnostic testing and ART costs for the study duration
- e. Retention in HIV clinical care at study completion
- f. 9-month mortality rate
- g. Change in health-related quality of life from baseline to 9 months

4. Efficacy Analysis Plan

Study data coordinators will perform routine reviews of data quality to identify unusual values and missing data entries. Initial analyses will include common exploratory data analyses, table construction, and scatterplots to assist in data quality control, randomization balance, and exploring for possible outliers or leverage points. For our analysis of the primary outcome, we will use a two-sample test of binomial proportions to compare the proportions of participants in each arm who achieve virologic suppression at the study conclusion. For our primary analysis we will conduct an intention to treat analysis. For this analysis, any study participant without a confirmed viral load result at the 9-month study endpoint will be considered as having a detectable viral load (failure). In secondary analyses, we will conduct as-treated analyses for any study participants who do not complete resistance testing in the RT arm or participant who do receive resistance testing in the SOC arm, as documented by clinic records. We will also conduct a sensitivity analysis by censoring participants who are lost-to-follow-up during study procedures and do not have a recorded viral load at study conclusion. The unadjusted comparison of outcome rates will be followed by adjusted comparisons via logistic regression, adjusting for other confounding factors that may explain any heterogeneity or possibly confound assigned treatment and outcome, despite treatment randomization.

The primary analyses will be followed by similar statistical analyses of secondary endpoints including the proportions suppressed on first-line therapy, rates of resistance, rates of retention in care, and the 9-month mortality rate. We will compare health related quality of life measures within participants between baseline and study conclusion using paired t-tests.

C. Economic Analyses

1. Budget Impact Analysis

The goal of this analysis is to estimate total projected costs for treatment programs, comparing the WHO standard of care versus a resistance-testing based approach to management of virologic failure. We will follow International Society of Pharmacoeconomics Outcomes Research (ISPOR) guidelines to develop models to determine the budget impact of adopting resistance testing in South Africa and Uganda, respectively ^[42]. We will populate each model with data provided by the clinical trial on costs of care, and add country-specific HIV epidemiology, demographic and expenditure data to estimate the budget impact of adopting resistance testing over five years for each strategy. We will build the model such that country-specific fields will be flexible to enable analysis with other countries, to facilitate policy planning

and decision-making. Results of this analysis will advise HIV program partners on the net resources required in each country to implement routine resistance testing over a 5-year period.

2. Cost Effectiveness Analysis

If the resistance testing intervention is superior or similar to the standard of care strategy, we will proceed with a full cost-effectiveness analysis. This analysis seeks to build upon prior analyses that have considered the economics of resistance testing in sub-Saharan Africa [22-24]. We will achieve this by incorporating primary efficacy, quality of life, and cost data from the clinical trial, and by estimating the cost utility of resistance testing versus standard of care by selecting quality adjusted life years (QALY) as our primary outcome of interest.

